### Risk related to the administration of dabigatran (Part 2)

In study 1160.60 a single dose of 600 mg dabigatran etexilate was well tolerated by healthy subjects [[U06-1614-01](#)]. Taking into account the dose proportional kinetics of dabigatran the well tolerated single dose of 600 mg provides a safety margin of 4 to the therapeutic dose of 150 mg, which is used in Part 2 of this trial.

Dabigatran etexilate is a sensitive substrate of intestinal P-glycoprotein (P-gp). The effect of several P-gp inhibitors has been tested in healthy subjects. The strongest effects have been seen with a single dose of verapamil (+180% in dabigatran  $C_{max}$ ) and with multiple doses of ketoconazole (+150% in dabigatran  $C_{max}$  und  $AUC$ ). The observed increase in dabigatran exposure has been well tolerated by healthy subjects (1160.74 and 1160.101), which is in line with the described safety margin of 4, that has not been exceeded by any P-gp inhibitor.

Verapamil and ketoconazole are well characterized inhibitors of P-gp and therefore recommended for testing P-gp inhibition [[P12-05791](#)]. Considering that the potential effect of BI 1358894 on the P-gp substrate dabigatran etexilate does not exceed the observed strong effect of verapamil or ketoconazole on dabigatran exposure and taking into account the overall safety margin of 4, which has not been exceeded by any P-gp inhibitor, no undue risk to healthy subjects is expected from the combined administration of 150 mg dabigatran etexilate and BI 1358894 in this trial.

### Drug-induced liver injury (DILI)

Although rare, a potential for drug-induced liver injury (DILI) is under constant surveillance by sponsors and regulators. Therefore, this trial requires timely detection, evaluation, and follow-up of laboratory alterations in selected liver laboratory parameters to ensure subjects' safety. See also Section [5.2.6.1.4](#), adverse events of special interest.

Proprietary confidential information © 2019 Boehringer Ingelheim International GmbH or one or more of its affiliated companies

**Overall assessment**

Considering the well characterised safety profile of the marketed drugs dabigatran and rosuvastatin, the safety profile observed so far with BI 1358894 and taking into account the planned single dose administration of all compounds the sponsor feels that the risk to participating subjects are minimised and justified when compared to the potential benefit that a successful clinical development of BI 1358894 could provide to the treatment of major depressive disorder and borderline personality disorder.

## **2. TRIAL OBJECTIVES AND ENDPOINTS**

### **2.1 MAIN OBJECTIVES, PRIMARY AND SECONDARY ENDPOINTS**

#### **2.1.1 Main objectives**

The main objective of this trial is to investigate the relative bioavailability of rosuvastatin (Reference 1, Part 1) and dabigatran (Reference 2, Part 2) given alone and together with BI 1358894 (Test 1, Test 2) following oral administration.

#### **2.1.2 Primary endpoints**

In Part 1 the following pharmacokinetic parameters will be determined for rosuvastatin:

- $AUC_{0-\infty}$  (area under the concentration-time curve of the analyte in plasma over the time interval from 0 extrapolated to infinity)
- $C_{max}$  (maximum measured concentration of the analyte in plasma)

In Part 2 the following pharmacokinetic parameters will be determined for dabigatran:

- $AUC_{0-\infty}$  (area under the concentration-time curve of the analyte in plasma over the time interval from 0 extrapolated to infinity)
- $C_{max}$  (maximum measured concentration of the analyte in plasma)

#### **2.1.3 Secondary endpoint**

In Part 1 the following pharmacokinetic parameter will be determined for rosuvastatin:

- $AUC_{0-tz}$  (area under the concentration-time curve of the analyte in plasma over the time interval from 0 to the last quantifiable data point)

In Part 2 the following pharmacokinetic parameter will be determined for dabigatran:

- $AUC_{0-tz}$  (area under the concentration-time curve of the analyte in plasma over the time interval from 0 to the last quantifiable data point)

#### **2.2.2.4 Safety and tolerability**

Safety and tolerability of rosuvastatin, dabigatran and BI 1358894 will be assessed based on:

- Adverse events (including clinically relevant findings from the physical examination)
- Safety laboratory tests
- 12-lead ECG
- Vital signs (blood pressure, pulse rate)

### 3. DESCRIPTION OF DESIGN AND TRIAL POPULATION

#### 3.1 OVERALL TRIAL DESIGN AND PLAN

The study consists of 2 trial parts. Each part follows a non-randomised, open-label, two-period crossover design with a fixed sequence in healthy male subjects in order to compare the following test and reference treatments:

##### Treatments in Part 1

- Reference (R1): tablet Crestor® Filmtabletten [rosuvastatin]
- Test (T1): tablet Crestor® Filmtabletten together with tablet BI 1358894

##### Treatments in Part 2

- Reference (R2): capsule Pradaxa® Hartkapseln [dabigatran etexilate]
- Test (T2): capsule Pradaxa® Hartkapseln together with tablet BI 1358894

All treatments will be given after a high-fat high-calorie breakfast. In both trial parts the Reference treatment will always be followed by the Test treatment in a fixed sequence. The treatment periods are separated by a wash-out phase of at least 7 days between the two drug administrations.

An overview of all relevant trial activities is provided in the [Flow Chart](#). For visit schedule and details of trial procedures at selected visits, refer to Sections [6.1](#) and [6.2](#), respectively.

#### 3.2 DISCUSSION OF TRIAL DESIGN, INCLUDING THE CHOICE OF CONTROL GROUPS

For relative bioavailability trials, the crossover design is preferred because of its efficiency: since each subject serves as his own control, the comparison between treatments is based on an intra-subject comparison, thus removing inter-subject variability from the comparison between treatments [\[R94-1529\]](#).

Because of the long terminal half-life of BI 1358894 (> 100 h), a fixed-sequence design was selected, in which BI 1358894 will be administered in the second study period only. The fixed-sequence design is not expected to lead to systematic errors in the estimation of the treatment effects since nonspecific time-effects are unlikely due to the short trial duration.

The open-label treatment is not expected to bias results, since the study endpoints are derived from measurement of plasma concentrations of the analyte.

#### 3.3 SELECTION OF TRIAL POPULATION

It is planned that 14 healthy male subjects each will enter either Part 1 or Part 2 of the study. They will be recruited from the volunteers' pool of the trial site. In case more than 2 subjects do not complete the respective trial part according to protocol, up to 6 replacement subjects may be included into each trial part. Thus, a maximum of 20 subjects might participate in each trial part.

Proprietary confidential information © 2019 Boehringer Ingelheim International GmbH or one or more of its affiliated companies

Only male subjects will be included in the study because no data on reproductive toxicology are available at this time.

A log of all subjects enrolled into the trial (i.e. who have signed informed consent) will be maintained in the ISF irrespective of whether they have been treated with investigational drug or not.

### **3.3.1 Main diagnosis for trial entry**

The study will be performed in healthy subjects.

### **3.3.2 Inclusion criteria**

Subjects will only be included in the trial if they meet the following criteria:

1. Healthy male subjects according to the assessment of the investigator, as based on a complete medical history including a physical examination, vital signs (BP, PR), 12-lead ECG, and clinical laboratory tests
2. Age of 18 to 55 years (inclusive)
3. BMI of 18.5 to 29.9 kg/m^2 (inclusive)
4. Signed and dated written informed consent prior to admission to the study, in accordance with GCP and local legislation

### **3.3.3 Exclusion criteria**

Subjects will not be allowed to participate, if any of the following general criteria apply:

1. Any finding in the medical examination (including BP, PR or ECG) deviating from normal and assessed as clinically relevant by the investigator
2. Repeated measurement of systolic blood pressure outside the range of 90 to 140 mmHg, diastolic blood pressure outside the range of 50 to 90 mmHg, or pulse rate outside the range of 45 to 90 bpm
3. Any laboratory value outside the reference range that the investigator considers to be of clinical relevance (including positive or missing faecal occult blood test in Part 2, retest allowed)
4. Any evidence of a concomitant disease assessed as clinically relevant by the investigator
5. Gastrointestinal, hepatic, renal, respiratory, cardiovascular, metabolic, immunological or hormonal disorders
6. Cholecystectomy or other surgery of the gastrointestinal tract that could interfere with the pharmacokinetics of the trial medication (except appendectomy or simple hernia repair)
7. Diseases of the central nervous system (including but not limited to any kind of seizures or stroke), and other relevant neurological or psychiatric disorders
8. History of relevant orthostatic hypotension, fainting spells, or blackouts
9. Chronic or relevant acute infections
10. History of relevant allergy or hypersensitivity (including allergy to the trial medication or its excipients)

Proprietary confidential information © 2019 Boehringer Ingelheim International GmbH or one or more of its affiliated companies

11. Use of drugs within 30 days of planned administration of trial medication that might reasonably influence the results of the trial (including drugs that cause QT/QTc interval prolongation)
12. Intake of an investigational drug in another clinical trial within 60 days of planned administration of investigational drug in the current trial, or concurrent participation in another clinical trial in which investigational drug is administered
13. Smoker (more than 10 cigarettes or 3 cigars or 3 pipes per day)
14. Inability to refrain from smoking on specified trial days
15. Alcohol abuse (consumption of more than 24 g per day)
16. Drug abuse or positive drug screening
17. Blood donation of more than 100 mL within 30 days of planned administration of trial medication or intended blood donation during the trial
18. Intention to perform excessive physical activities within one week prior to the administration of trial medication or during the trial
19. Inability to comply with the dietary regimen of the trial site
20. A marked prolongation of QTc interval (such as QTc intervals that are repeatedly greater than 450 ms) or any other relevant ECG finding at screening
21. A history of additional risk factors for *Torsade de Pointes* (such as heart failure, hypokalaemia, or family history of Long QT Syndrome)
22. Subject is assessed as unsuitable for inclusion by the investigator, for instance, because the subject is not considered able to understand and comply with study requirements, or has a condition that would not allow safe participation in the study
23. Male subjects with WOCBP partner who are unwilling to use male contraception (condom or sexual abstinence) from time point of administration of trial medication until 30 days thereafter. Sperm donation is not allowed from the time point of drug administration until 30 days thereafter.

The following study specific exclusion criteria apply:

24. Known hypersensitivity to rosuvastatin or dabigatran
25. Active liver disease including elevations of serum transaminases exceeding 2 times the upper limit of normal
26. Moderate or severe renal impairment (creatinine clearance < 60 ml/min based on estimated GFR according to CKD-EPI formula)
27. Known myopathy
28. Concomitant treatment with systemic cyclosporine, ketoconazole, itraconazole and dronedarone or use of fibrates
29. Hypothyroidism
30. Personal or family history of hereditary muscular disorders
31. History of muscular toxicity with another statin or fibrate
32. Asian ancestry
33. Known active bleeding

Proprietary confidential information © 2019 Boehringer Ingelheim International GmbH or one or more of its affiliated companies

34. Concomitant treatment with other anticoagulants (e.g. unfractionated heparin, low molecular weight heparins, heparin derivatives, oral anticoagulants)
35. Prosthetic heart valves
36. Subjects who in the investigator's judgement are perceived as having an increased risk of bleeding, for example because of: current or recent gastrointestinal ulceration, presence of malignant neoplasms, recent brain or spinal injury, recent brain / spinal/ ophthalmic surgery, recent intracranial hemorrhage, known or suspected oesophageal varices, arteriovenous malformations, vascular aneurysms, major intraspinal or intracerebral vascular abnormalities

For study restrictions, refer to Section [4.2.2](#).

### **3.3.4 Withdrawal of subjects from treatment or assessments**

Subjects may discontinue trial treatment or withdraw consent to trial participation as a whole ('withdrawal of consent') with very different implications; please see Sections [3.3.4.1](#) and [3.3.4.2](#) below.

If a subject is removed from or withdraws from the trial prior to the first administration of trial medication, the data of this subject will not be entered in the case report form (CRF) and will not be reported in the clinical trial report (CTR). If a subject is removed from or withdraws from the trial after the first administration of trial medication, this will be documented and the reason for discontinuation must be recorded in the CRF; in addition, the data will be included in the CRF and will be reported in the CTR. At the time of discontinuation, a complete end of trial examination will be performed, if possible, and the information will be recorded in the CRF. If the discontinuation occurs before the end of the REP (see Section [1.2.4](#)), the discontinued subject should if possible be questioned for AEs and concomitant therapies at or after the end of the REP in order to ensure collection of AEs and concomitant therapies throughout the REP, if not contrary to any consent withdrawal of the subject.

#### **3.3.4.1 Discontinuation of trial treatment**

An individual subject will discontinue trial treatment if:

1. The subject wants to discontinue trial treatment, without the need to justify the decision
2. The subject has repeatedly shown to be non-compliant with important trial procedures and, in the opinion of both, the investigator and sponsor representative, is not willing or able to adhere to the trial requirements in the future.
3. The subject needs to take concomitant medication that interferes with the investigational medicinal product or other trial treatment
4. The subject can no longer receive trial treatment for medical reasons (such as surgery, adverse events [AEs], or diseases)
5. The subject has an elevation of AST and/or ALT  $\geq 3$ -fold ULN and an elevation of total bilirubin  $\geq 2$ -fold ULN (measured in the same blood sample) and/or needs to be followed up according to the DILI checklist provided in the ISF

Proprietary confidential information © 2019 Boehringer Ingelheim International GmbH or one or more of its affiliated companies

In addition to these criteria, the investigator may discontinue subjects at any time based on his or her clinical judgment.

Even if the trial treatment is discontinued, the subject remains in the trial and, given his/her agreement, will undergo the procedures for early treatment discontinuation and follow up as outlined in the [Flow Chart](#) and Section [6.2.3](#).

#### **3.3.4.2 Withdrawal of consent to trial participation**

Subjects may withdraw their consent to trial participation at any time without the need to justify the decision. If a subject wants to withdraw consent, the investigator should be involved in the discussion with the subject and explain the difference between trial treatment discontinuation and withdrawal of consent to trial participation, as well as explain the options for continued follow up after trial treatment discontinuation, please see section [3.3.4.1](#) above.

#### **3.3.4.3 Discontinuation of the trial by the sponsor**

Boehringer Ingelheim reserves the right to discontinue the trial at any time for any of the following reasons:

1. New toxicological findings, serious adverse events, or any safety information invalidating the earlier positive benefit-risk-assessment. More specifically, the trial will be terminated if more than 50% of the subjects have drug-related and clinically relevant adverse events of moderate or severe intensity, if at least 2 subjects of the same cohort have drug-related severe non-serious adverse events, or if at least 1 drug-related serious adverse event is reported
2. Violation of GCP, or the CTP impairing the appropriate conduct of the trial
3. The sponsor decides to discontinue the further development of the investigational product

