#### **3.3.5 Replacement of subjects**

In case more than 2 subjects do not complete the respective trial part according protocol for any reason (including non PK evaluable subjects), the Clinical Trial Leader together with the Trial Pharmacokineticist and the Trial Statistician are to decide, if and how many subjects will be replaced. The maximum number of replacement subjects is 6 per trial part. Thus the total number of exposed subjects will not exceed 20 in each trial part. A replacement subject will be assigned a unique trial subject number.

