#### 4.1.3 Method of assigning subjects to treatment groups

There is only one treatment sequence investigated in each trial part, and each subject will be allocated to the same treatment sequence (R-T). The subjects will be allocated to a study subject number by drawing lots prior to first administration of trial medication in the morning of Day 1 of Visit 2. Once a subject number has been assigned, it cannot be reassigned to any other subject.

All subjects of the respective study part may be treated in one cohort, i.e. all subjects may receive treatment on the same calendar day. In case this is not feasible (e.g., due to logistical or recruitment reasons), the group may be split into several cohorts as required. Treatment of all subjects on the same calendar day is acceptable (for discussion of study-associated risks see Section 1.4).

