## 7. PLANNED ANALYSIS

If not stated otherwise, the trial parts will be evaluated separately.

Safety analysis (refer to [Section 7.8](#)) will be performed by \_\_\_\_\_ and will be presented in Sections 15.1 to 15.4 of the CTR and in Appendix 16.2 and 16.1.13.1.

Inferential statistical analyses of PK endpoints (refer to [Section 7.4](#) and [Section 7.5.2](#)) will also be performed by \_\_\_\_\_ and will be presented in Section 15.5 of the CTR and in Appendix 16.1.13.3.

Descriptive data analysis of PK/PD endpoints and concentrations will be performed by the \_\_\_\_\_ at \_\_\_\_\_ and will be presented in Section 15.6 and Section 15.7 of the CTR.

The format of the listings and tables will follow the BI standards (see BI-KMED-BDS-HTG-0045 ([6](#))) with the exception of those generated for PK-calculations ([7](#)).

The individual values of all subjects will be listed, sorted by sequence group, subject number, visit and actual treatment (if appropriate).

The listings will be included in Appendix 16.2 of the CTR.

For end-of-text tables, the set of summary statistics for non-PK parameters is:

N	number non-missing observations
Mean	arithmetic mean
SD	standard deviation
Min	minimum
Median	median
Max	maximum

For analyte concentrations, the following descriptive statistics will additionally be calculated:

CV	arithmetic coefficient of variation
gMean	geometric mean
gCV	geometric coefficient of variation

For PK/PD parameters, the following descriptive statistics will additionally be calculated:

CV	arithmetic coefficient of variation
gMean	geometric mean
gCV	geometric coefficient of variation
P10	10th percentile
Q1	1st quartile
Q3	3rd quartile
P90	90th percentile

The data format for descriptive statistics of concentrations will be identical to the data format of the respective concentrations. The descriptive statistics of PK parameters will be calculated using the individual values with the number of decimal places as provided by the evaluation program. Then the individual values as well as the descriptive statistics will be reported with three significant digits in the CTR.

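### The mandatory stop for two severe drug-related adverse events counts within a dosing-day cohort, so in a split part or with later replacements it depends on scheduling

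*Protocol*

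**What the plan says.** Protocol section 3.3.4.3 lists three conditions under which the trial must end:

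- A proportion rule: "the trial will be terminated if more than 50% of the subjects have drug-related and clinically relevant adverse events of moderate or severe intensity".
- A count rule: "if at least 2 subjects of the same cohort have drug-related severe non-serious adverse events".
- A single drug-related serious adverse event.

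Only the count rule refers to a cohort. The same item also gives the sponsor a general right to stop for "any safety information invalidating the earlier positive benefit-risk-assessment".

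The term is not formally defined. Section 4.1.3 is the only place that explains it: "All subjects of the respective study part may be treated in one cohort, i.e. all subjects may receive treatment on the same calendar day". If one-day dosing is not feasible, "the group may be split into several cohorts as required". The number and size of such cohorts are left open. The same section gives every subject of a part one fixed sequence, reference then test.

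Section 3.3.5 allows up to 6 replacements per part once more than 2 subjects fail to complete it, so that "the total number of exposed subjects will not exceed 20 in each trial part". It does not say to which cohort a replacement belongs. The SAP does not address the stopping rule. Its section 7 takes the part as the unit of analysis: "If not stated otherwise, the trial parts will be evaluated separately".

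**The concern.** Counting adverse events within a cohort makes sense where cohorts differ in exposure, as in dose escalation. Here they do not: within a part there is one dose of each drug and one sequence, and a cohort is only a group dosed on the same day. Two severe drug-related non-serious events are the same safety signal whether the subjects were dosed together or on different days, yet the literal rule treats the two cases differently.

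The same applies to one of the first 14 subjects and a replacement. Replacement is decided only after others have failed to complete or proved not evaluable, so a later dosing day is to be expected.

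What is at stake is the automatic nature of the stop. A rule that prescribes termination exists to take the decision out of discretion. In a split part it can lapse for a purely logistical reason, leaving the decision to the sponsor's general clause.

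**Working it through.** The documents give no operating characteristic for the stopping rule, so there is no planned figure to reproduce.

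**Inputs.** 14 subjects per part (protocol 3.3), at most 6 replacements and 20 exposed per part (3.3.5), and a threshold of 2 subjects within one cohort (3.3.4.3). The splits 7+7, 10+4 and 5+5+4, and the choice of 3 or 6 replacements dosed on a single later day, are illustrations. The protocol fixes none of them.

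**Step 1: no adverse event rate needed.** Suppose exactly 2 of the n subjects are affected, at random. The chance that both fall in the same cohort, with cohort sizes m_i, is the sum of C(m_i,2) divided by C(n,2).

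| Cohorts | Calculation | Trigger fires |
|---|---|---|
| 14 | 91/91 | 100% |
| 10+4 | (45+6)/91 = 51/91 | 56.0% |
| 7+7 | (21+21)/91 = 42/91 | 46.2% |
| 5+5+4 | (10+10+6)/91 = 26/91 | 28.6% |
| 14+3 replacements | (91+3)/136 = 94/136 | 69.1% |
| 14+6 replacements | (91+15)/190 = 106/190 | 55.8% |

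**Step 2: with an assumed rate.** The documents give no rate of severe drug-related non-serious events. Let q be the per-subject risk, equal and independent across subjects. Then

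P(fires) = 1 − product over cohorts of P(X ≤ 1 | m_i, q), with X binomial.

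At q = 10%, one cohort of 14: P(X ≤ 1) = 0.9^14 + 14 × 0.1 × 0.9^13 = 0.229 + 0.356 = 0.585, so P(fires) = 41.5%. For 7+7, each cohort has P(X ≤ 1) = 0.9^7 + 7 × 0.1 × 0.9^6 = 0.478 + 0.372 = 0.850, so P(fires) = 1 − 0.850² = 27.7%.

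| Assumed q | 14 in one cohort | 7+7 | 5+5+4 | 14+6, separate cohorts | 20 counted together |
|---|---|---|---|---|---|
| 2% | 3.1% | 1.6% | 1.0% | 3.7% | 6.0% |
| 5% | 15.3% | 8.7% | 5.8% | 18.1% | 26.4% |
| 10% | 41.5% | 27.7% | 20.0% | 48.2% | 60.8% |
| 20% | 80.2% | 66.7% | 55.5% | 87.0% | 93.1% |

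**Step 3: do the other triggers cover the gap?** The serious-event trigger does not, because the count rule concerns non-serious events. The proportion rule needs more than half: even if counted per part, that is at least 8 of 14 subjects. Neither is met by two severe non-serious events alone.

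**The case against.** The case for leaving the text alone has several parts.

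- **Reading.** Section 4.1.3 uses the term for dosing logistics, and neither section refers to the other, so the authors may have meant the trial part. That is possible. The amendment would then only write down the intent, and site and sponsor still need one reading of a mandatory safety rule.
- **Conditionality.** Single-day dosing is named first, with splitting as the fallback, and replacement needs more than 2 non-completers. Without either, cohort and part coincide. This stands and limits the concern. That replacements form their own cohort is also an inference from the same-day wording.
- **Safeguards.** The sponsor may stop at any time on safety grounds, and the investigator may discontinue any subject (3.3.4.1). This stands too: what is lost is the automatic stop, not the ability to stop.
- **Magnitude.** The rates of 2% to 20% are assumptions. The protocol describes adverse events with dabigatran in healthy volunteers as few and mild (1.2.3) and 10 mg rosuvastatin as well tolerated (1.4), so the upper end has no support in what can be read. At 2% the 7+7 split costs only 1.5 percentage points. The figures in step 1 avoid a rate but presuppose two affected subjects.
- **Exposure.** The 14+3 and 14+6 figures assume that everyone received the treatment counted. Subjects who leave before Period 2 never receive BI 1358894, so these figures need not hold for events on the test treatment.
- **Choice of unit.** A trial part pools reference and test periods, and one severe event in each part would still not fire. The trial part is therefore not the only defensible unit, but it removes the dependence on dosing day.

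**Conclusion.** The concern holds. On the only explanation of a cohort in the documents, the same two severe drug-related non-serious events do or do not force termination depending on the dosing calendar, although all subjects of a part receive the same treatments. Given exactly two affected subjects out of 14 at random, the chance of an automatic stop falls from 100% to 56.0% (10+4) or 46.2% (7+7). Over assumed risks of 2% to 20%, the 7+7 split lowers the unconditional probability by between 1.5 points (at 2%) and 13.8 points (at 10%, 41.5% against 27.7%).

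This rests on the literal reading, on a part being split or replacements being dosed on another day, and, for the unconditional figures, on independent and equal risks that the documents do not supply. No endpoint, estimate or confidence interval is affected. The change is worth making because it is small and concerns a stated safety rule. It is not critical to the validity of the trial.

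**What to change.** In protocol section 3.3.4.3, count the two subjects within the same trial part, including replacement subjects, instead of within the same cohort. The part already defines the treatments given and is the default unit of analysis in SAP section 7. The revised rule gives the same result as the present one when a part is dosed on one day without replacements.

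The edit is one phrase and needs no extra subjects or data. As a change to a stopping criterion it would need ethics committee and authority approval (section 8.1), as Amendment 1 did. The operating cost is a trigger that fires more often when a part is split or subjects are replaced: at an assumed 10% risk, 41.5% instead of 27.7% for 7+7, and 60.8% instead of 48.2% for 14+6.
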